9.9 Vital Signs

Vital signs (oral temperature, pulse, respiratory rate, and seated blood pressure) will be measured at the Screening Visit (Day -14 to Day -1), the Baseline Visit (Day 1), and Weeks 2, 4, 8, 12, and 16.

Blood pressure will be measured using a standardized process:

- Patient should sit for 5 minutes with feet flat on the floor and measurement arm supported so that the midpoint of the manometer cuff is at heart level;
- Use of a mercury sphygmomanometer or automatic blood pressure device with an appropriately sized cuff with the bladder centered over the brachial artery;
- Record the arm used for measurement and use the same arm throughout the study; and
- Measure and record the blood pressure.

Blood pressure should be recorded to the nearest 2 mmHg mark on the manometer or to the nearest whole number on the automatic device. A blood pressure reading should be repeated 1 to 2 minutes later, and the second reading should also be recorded to the nearest 2 mmHg mark.

Body weight will be measured at the Screening Visit (Day -14 to Day -1), the Baseline Visit (Day 1), and Weeks 2, 4, 8, 12, and 16. Height will be recorded at the Screening Visit and Weeks 2, 4, and 8. Body weight measurement should be performed with the patient dressed in indoor clothing, shoes removed, and bladder empty. Patients should be weighed on the same scale at all visits. Height measurement should be performed with the patient's shoes removed; the patient's knees should be straightened, head held erect, and eyes forward.

9.10 Electrocardiograms

Twelve-lead ECGs with rhythm strip will be performed at the Screening Visit (Day -14 to Day -1), the Baseline Visit (Day 1), and Weeks 2, 4, 8, 12, and 16. At the Week 2 visit, patients will rest for 30 minutes after the 4 h post-dose blood draw before the ECG is performed.

Twelve-lead ECGs will be performed in triplicate in a consecutive manner after the patient has been resting in the supine position for at least 10 minutes. The ECG will include 12 standard leads and will be recorded at a paper speed of 25 mm/sec. The following ECG parameters will be recorded:

- PR interval,
- QRS interval,
- Heart rate,
- RR interval,
- QT interval,
- QTc interval, and
- QTcF interval.

All ECGs must be evaluated by a qualified reader for the presence of abnormalities.

9.11 Physical Examinations

A complete physical examination will include documentation of general appearance, skin, and specific head and neck, heart, lung, abdomen, extremities, and neuromuscular assessments and will be performed at the Screening Visit (Day -14 to Day -1). Targeted, symptom-directed physical examinations will be performed at all other study visits.

9.12 Diet and Lifestyle Counseling

Patients will be counseled on maintaining a consistent diet, exercise regimen, and lifestyle at the Screening Visit (Day -14 to Day -1).

9.13 Drug Induced Liver Injury Monitoring

With any of the following liver function test elevations, patients should undergo repeat laboratory measurements as soon as possible, preferably within 72 hours (unless otherwise specified), and no later than 1 week. Local laboratory measurements may be used to facilitate follow-up:

- ALT or AST $>8 \times$ ULN;
- ALT or AST $>3 \times$ ULN and bilirubin $>2 \times$ ULN or International Normalized Ratio $>1.5 \times$ ULN;
- ALT or AST $>3 \times$ ULN with the appearance of fatigue, nausea, vomiting, right upper quadrant pain or tenderness, fever rash, and/or eosinophilia ($>5\%$); and
- ALT or AST $>5 \times$ ULN, regardless of symptoms should be followed up within 1 week.

Repeat evaluation should include AST, ALT, prothrombin time/International Normalized Ratio, total bilirubin, alkaline phosphatase, gamma-glutamyltransferase, creatinine, CK, and complete viral hepatitis screen. The patient should be questioned regarding symptoms, as well as potential causative factors. This information, including results and normal ranges of any laboratory parameters collected at a local laboratory, should be collected on the appropriate eCRF. Hepatobiliary ultrasonography and/or consultation with a hepatologist should be considered if clinically indicated.

Abnormal laboratory parameters should be followed at least weekly (more frequently as clinically indicated) until they have returned to baseline or have stabilized.

10 STATISTICS

10.1 Analysis Populations

The Intent-to-Treat (ITT) Population will include all patients who are randomized in the study and receive at least 1 dose of study drug. The ITT Population will be used for all efficacy analyses.

The Per Protocol Population will include all ITT patients who finish the Week 12 Visit with valid LDL-C measurements, have $\geq 80\%$ treatment compliance, and do not have any major protocol deviations.

The Safety Population will include all patients who are randomized in the study and receive at least 1 dose of study drug and will be used for all safety analyses.

For patients randomized to MGL-3196, the assigned treatment group (60 or 100 mg group) will be based on the dose at Week 4 to Week 12.

10.2 Statistical Methods

10.2.1 Analysis of Efficacy

10.2.1.1 Primary efficacy analysis

The primary efficacy variable will be the change in LDL-C from baseline to Week 12. Summary statistics (number of patients, mean, standard deviation, median, minimum, and maximum) at all visits and change from baseline will be provided. The primary efficacy analysis will be analyzed with an analysis of covariance (ANCOVA) model with treatment as a factor and baseline LDL-C as a covariate. Determinations for the 100 (and 60) mg groups will be based on all 12 weeks of the study, including the first two weeks (Week 0-2) in which all patients were on 100 mg and the second two weeks (Week 2-4) when all patients down-titrated to 60 mg. The assigned group (60 or 100 mg) will be based on the dose at Week 4 to Week 12. For any patients in the ITT Population with a missing primary efficacy parameter, the last observation carried forward method will be used. The multiplicity (MGL-3196 100 mg versus placebo and MGL-3196 60 mg versus placebo) will be controlled by Dunnett's Test. The primary efficacy analysis will be performed based on the ITT Population and repeated based on the Per Protocol Population.

10.2.1.2 Secondary efficacy analysis

For the continuous secondary efficacy variables, the same ANCOVA model will be used. Normality will be tested for the model residuals. For certain efficacy variables, logarithm transformation may be performed prior to fitting the ANCOVA model. For the categorical secondary efficacy variables, Fisher's exact test will be used to compare the odds ratio between MGL-3196 doses versus placebo.

10.2.1.3 Other efficacy analysis

The same efficacy analyses used for the secondary efficacy variables will be used for any potential exploratory efficacy variables.

10.2.1.4 Subgroup analysis

Subgroup analysis of the primary efficacy variable and/or selected secondary/other efficacy variables may be performed, such as gender (male/female), body mass index (≥ 30 kg/m² or < 30 kg/m²), age group (\geq median or $<$ median), and baseline thyroid status.

10.2.2 Analysis of Safety

The safety endpoints for this study include: safety laboratory tests, vital signs, 12-lead ECGs, physical examinations, assessment of adverse events, and clinic assessments.

The adverse events will be coded using the latest version of the Medical Dictionary for Regulatory Activities (MedDRA). Treatment-emergent adverse events (TEAEs) will be defined as adverse events that are new or worsening after the first dose of study drug. A general summary of patients with TEAEs and SAEs will be tabulated with numbers and percentages of patients, and repeated for severity and relationship to study drug per treatment group. The number of adverse events leading to withdrawal and SAEs leading to death will also be summarized. The incidence of TEAEs will be summarized by body system and treatment group.

The safety laboratory data will be summarized by visit and by treatment group, along with changes from the baseline. The values that are $<$ LLN or $>$ ULN of the reference range will be flagged. Those values or changes in values that are identified as being clinically significant will be flagged. Laboratory abnormalities of special interest will be summarized.

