9 SAFETY ASSESSMENTS

9.1 Adverse Events

An adverse event is defined as any untoward medical occurrence in a clinical investigation patient administered a pharmaceutical product, which does not necessarily have a causal relationship with this treatment. An adverse event can therefore be any unfavorable and/or unintended sign (including an abnormal laboratory finding), symptom, or disease temporally associated with the use of an investigational medicinal product, whether or not related to the investigational medicinal product. All adverse events, including observed or volunteered problems, complaints, or symptoms, are to be recorded on the appropriate eCRF.

Adverse events, which include clinical laboratory test variables, will be monitored and documented from the time of informed consent until study participation is complete. Patients should be instructed to report any adverse event that they experience to the Investigator. Beginning at the Screening Visit, Investigators should make an assessment for adverse events at each visit and record the event on the appropriate adverse event eCRF.

Wherever possible, a specific disease or syndrome rather than individual associated signs and symptoms should be identified by the Investigator and recorded on the eCRF. However, if an observed or reported sign or symptom is not considered a component of a specific disease or syndrome by the Investigator, it should be recorded as a separate adverse event on the eCRF. Additionally, the condition that led to a medical or surgical procedure (eg, surgery, endoscopy, tooth extraction, or transfusion) should be recorded as an adverse event, not the procedure.

Any medical condition already present at screening should not be reported as an adverse event unless the medical condition or signs or symptoms present at baseline change in severity or seriousness at any time during the study. In this case, it should be reported as an adverse event.

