9.1.3 Assessment of Adverse Events by the Investigator

The Investigator will assess the severity (intensity) of each adverse event as mild, moderate, or severe, and will also categorize each adverse event as to its potential relationship to study drug using the categories of yes/no.

Assessment of Severity:

Mild – An event that is easily tolerated and generally not interfering with normal daily activities.

Moderate – An event that is sufficiently discomforting to interfere with normal daily activities.

Severe – An event that is incapacitating with inability to work or perform normal daily activities.

Causality Assessment:

The relationship of an adverse event to the administration of the study drug is to be assessed according to the following definitions:

No (unrelated, not related, no relation) – The time course between the administration of study drug and the occurrence or worsening of the adverse event rules out a causal relationship and another cause (concomitant drugs, therapies, complications, etc.) is suspected.

Yes (related) – The time course between the administration of study drug and the occurrence or worsening of the adverse event is consistent with a causal relationship and no other cause (concomitant drugs, therapies, complications, etc.) can be identified.

The definition implies a reasonable possibility of a causal relationship between the event and the study drug. This means that there are facts (evidence) or arguments to suggest a causal relationship.

The following factors should also be considered:

- The temporal sequence from study drug administration-
 - The event should occur after the study drug is given. The length of time from study drug exposure to event should be evaluated in the clinical context of the event.
- Underlying, concomitant, intercurrent diseases-
 - Each report should be evaluated in the context of the natural history and course of the disease being treated and any other disease the patient may have.
- Concomitant drug-
 - The other drugs the patient is taking or the treatment the patient receives should be examined to determine whether any of them might be recognized to cause the event in question.
- Known response pattern for this class of study drug-
 - Clinical and/or preclinical data may indicate whether a particular response is likely to be a class effect.
- Exposure to physical and/or mental stresses-

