9.2 Serious Adverse Events

An adverse event or adverse reaction is considered serious if, in the view of either the Investigator or Sponsor, it results in any of the following outcomes:

- Death;
- A life-threatening adverse event;
 - Note: An adverse event or adverse reaction is considered “life-threatening” if, in the view of either the Investigator or Sponsor, its occurrence places the patient at immediate risk of death. It does not include an event that, had it occurred in a more severe form, might have caused death.
- Requires hospitalization or prolongation of existing hospitalization;
 - Note: Any hospital admission with at least 1 overnight stay will be considered an inpatient hospitalization. An emergency room visit without hospital admission will not be recorded as a SAE under this criterion, nor will hospitalization for a procedure scheduled or planned before signing of informed consent. However, unexpected complications and/or prolongation of hospitalization that occur during elective surgery should be recorded as adverse events and assessed for seriousness. Admission to the hospital for social or situational reasons (ie, no place to stay, live too far away to come for hospital visits) will not be considered inpatient hospitalizations.
- A persistent or significant disability/incapacity or substantial disruption of the ability to conduct normal life functions;
- A congenital anomaly/birth defect; or
- An important medical event.
 - NOTE: Important medical events that may not result in death, be life-threatening, or require hospitalization may be considered an SAE when, based upon appropriate medical judgment, they may jeopardize the patient and may require medical or surgical intervention to prevent one of the outcomes listed above. Examples of such medical events include allergic bronchospasm requiring intensive treatment in an emergency room or at home, blood dyscrasias or convulsions that do not result in inpatient hospitalizations, or the development of drug dependency.

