3.8.1 Adverse Events

Treatment-Emergent Adverse Events (TEAEs) are defined as adverse events that are new or worsen after the first dose of study drug. AE worsening applies to severity or relationship to study drug.

A summary overview of TEAEs will be provided, which presents the number and percentage of patients in each treatment group from the Safety Population satisfying each of the following categories:

- Any TEAEs,
- Maximum severity of TEAEs,
- Study drug-related TEAEs,
- Maximum severity of study drug-related TEAEs,
- All treatment-emergent serious adverse events (SAEs),
- All study drug-related TE-SAEs,
- TEAEs leading to death,
- TEAEs leading to study drug discontinuation, and
- Study drug-related TEAEs leading to study drug discontinuation.

Adverse events will be coded using MedDRA. The number and percentage of patients with TEAEs will be summarized by their MedDRA preferred term within system organ class and by treatment. AEs will be counted by the number of events as well as the number of patients. For event count summaries, multiple AE events with the same MedDRA coded terms (preferred term and system organ class) and onset date and time from the same patient will only be counted once. For patient count summaries, multiple AE events with the same MedDRA coded terms (preferred term and system organ class) from the same patient will only be counted once.

The number and percentage of patients with TEAEs will be summarized by reported maximum severity within each MedDRA preferred term within system organ class and by treatment.

The number and percentage of patients with TE-SAEs, any drug-related TEAEs, drug-related TE-SAEs, and TEAEs and TE-SAEs that lead to study drug discontinuation will be summarized by preferred term within system organ class and by treatment. In these summaries, any patients reporting multiple episodes of the same TEAE (i.e., same preferred term and system organ class) will be counted once.

All SAEs will be listed with an indication of whether the SAE was treatment emergent or started prior to treatment.

All TEAEs that are reported as leading to study drug discontinuation will be listed.

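### SAP 3.8.1 leaves seriousness out of its definition of worsening, so an adverse event that starts before dosing and turns serious afterwards can miss the treatment-emergent SAE counts

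*Protocol*

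**What the plan says.** The two documents share a parent definition. Protocol 10.2.2 has "Treatment-emergent adverse events (TEAEs) will be defined as adverse events that are new or worsening after the first dose of study drug", and SAP 3.8.1 has "Treatment-Emergent Adverse Events (TEAEs) are defined as adverse events that are new or worsen after the first dose of study drug". Only the SAP goes on to define worsening: "AE worsening applies to severity or relationship to study drug".

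Four other provisions bear on that sentence.

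- **Collection period (protocol 9.1).** Adverse events "will be monitored and documented from the time of informed consent until study participation is complete". Screening runs from Day -14 to Day -1, so adverse event records can exist before the first dose.
- **Conditions already present (protocol 9.1).** These are not reported as adverse events "unless the medical condition or signs or symptoms present at baseline change in severity or seriousness at any time during the study".
- **Severity (protocol 9.1.3).** "The Investigator will assess the severity (intensity) of each adverse event as mild, moderate, or severe".
- **Seriousness (protocol 9.2).** This is judged by outcome. One criterion is "Requires hospitalization or prolongation of existing hospitalization"; death and a life-threatening event are others.

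For reporting, SAP 3.8.1 limits its SAE overview rows and its table by system organ class and preferred term to treatment-emergent SAEs, and limits its death row to treatment-emergent events. It also lists every SAE, with a flag for treatment-emergent or started before treatment. Protocol 10.2.2 plans a summary of SAEs, and of SAEs leading to death, without restricting either to treatment-emergent events.

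**The concern.** A treatment-emergent SAE table is meant to show what became serious while patients were on study drug. The SAP's rule for an event that began before dosing looks at two attributes, severity grade and attributed relationship, and at neither the fact nor the timing of its becoming serious. Because severity and seriousness are separate attributes in this protocol, a hospitalisation on study drug can leave the grade where it was. The rule would then leave a post-dose serious outcome out of the counts and percentages that readers consult first. Safety and tolerability are the first secondary objective, and the arms are small enough for one SAE to show in a sparse table.

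**Working it through.** The plan has no figure to reproduce here. The check is a reading of the rules against one case, followed by simple arithmetic on size.

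**The case.** An adverse event starts between consent and Day 1. After the first dose it leads to an overnight hospital admission. The investigator keeps the same severity grade and still judges it unrelated. I assume it stays one adverse event record with its pre-dose onset date; the protocol does not say whether a site should open a new record when such an event turns serious.

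**Applying SAP 3.8.1.**

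1. Is it new after first dose? No, because onset was before dosing.
2. Has severity worsened? No, because the grade is unchanged.
3. Has relationship worsened? No, because it is still judged unrelated.
4. It is therefore not a treatment-emergent event, and so not a treatment-emergent SAE.
5. It is absent from the treatment-emergent SAE overview row and from the table by system organ class and preferred term. It appears in the all-SAE listing, flagged as started before treatment.

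**Can seriousness change without the grade changing?** Yes. Severity in protocol 9.1.3 measures interference with daily activity; seriousness in 9.2 is met by an outcome such as admission. The scale also stops at severe. An event already graded severe before dosing cannot rise further, so if it becomes life-threatening or fatal on study drug the severity criterion cannot register it. If relationship is also unchanged, a fatal case would miss the SAP's row for treatment-emergent events leading to death.

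**How the provisions compare.**

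| Provision | What it governs | Is a change in seriousness recognised? |
|---|---|---|
| Protocol 9.1 | When a condition already present is reported | Yes |
| Protocol 10.2.2 | Treatment-emergent definition | Not specified; worsening is undefined |
| Protocol 10.2.2 | SAE summary | Not limited to treatment-emergent events |
| SAP 3.8.1 | Meaning of worsening | No; severity or relationship only |

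**Size.** The documents give no rate of adverse events in screening. Assume that 5% to 20% of the 105 planned patients have one:

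- 0.05 × 105 = 5.25, about 5 patients
- 0.20 × 105 = 21 patients

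So about 5 to 21 patients would have an event that the rule has to classify. Only those whose event turns serious with grade and relationship unchanged are affected. I put that at 0 to 1, as a judgement and not a calculation. The weight of one event is:

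- MGL-3196 arm: 1/70 = 1.4 percentage points
- placebo arm: 1/35 = 2.9 percentage points

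**The case against.** The case for leaving the SAP as it is has several parts, and most of it limits the point without removing it.

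- **Protocol 9.1 is a reporting rule.** A reader might infer that the SAP contradicts a protocol definition of treatment emergence. It does not: 9.1 says when a condition already present becomes an adverse event, and 10.2.2 leaves worsening undefined and contains no error. Section 9.1 also narrows the gap. A medical-history condition that turns serious on study drug is first reported as an adverse event at that time and can count as new. What remains is events with onset between consent and first dose.
- **The relationship criterion already catches some cases.** Protocol 9.1.3 expects a related event to follow dosing, so a pre-dose event should start as unrelated. If it turns serious and is then attributed to study drug, the SAP counts it. The gap is confined to events still judged unrelated, so the drug-related SAE rows should not be affected.
- **Should relationship be removed from the definition?** A reader might infer this, since attribution is not in itself a change in the patient. The documents do not compel it. In 9.1.3 a related judgement rests on the timing of occurrence or worsening relative to dosing, and for a pre-dose event only worsening can follow dosing. Counting such events is a conservative choice, and deleting the criterion is a matter of preference.
- **Many admissions would also raise the grade.** Severe means incapacitating, so an event that leads to an overnight stay will often move up and count as worsened. That is fair, but it does not cover events that stay at the same grade or were already severe.
- **The event remains visible.** Every SAE is reported within 24 hours, the DSMB reviews safety data, and all SAEs are listed. This stands. What is lost is a place in the counts and percentages.

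**Conclusion.** The point holds in a narrow form. SAP 3.8.1 states a rule under which an adverse event that begins between consent and first dose, and becomes serious after first dose with grade and relationship unchanged, is left out of the treatment-emergent SAE counts and possibly out of the death row. This is a flaw in a stated rule and not merely missing detail. It also makes the SAP's tables narrower than the SAE summary planned in protocol 10.2.2.

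The expected size is 0 to 1 events. That rests on the assumed screening-period rate, on the judgement that few such events turn serious with nothing else changing, and on a site keeping one record for the event. A reader might infer that the safety comparison between arms would be distorted. The documents do not support that: the adverse event summaries are descriptive counts and percentages, the number at stake is about one at most, and the event is still listed. This is a low-priority correction, worth making because it is nearly free.

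**What to change.** In SAP 3.8.1, extend the sentence on worsening so that it also covers a change from non-serious to serious on or after the first dose of study drug. State that such an event counts as a treatment-emergent SAE and, if fatal, as a treatment-emergent event leading to death. Severity and relationship can stay as they are, and protocol 10.2.2 needs no edit.

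The cost is one SAP sentence and one derived flag, which needs the date on which an event became serious. The treatment-emergent SAE count may rise by an event. The change should be settled before unblinding so that the classification cannot be questioned afterwards.
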